16.2.8.2 Vital Signs**Listing 27: 16.2.8.2.1: Vital Signs**

[Implementation Note: This listing includes all vital sign assessments, scheduled and unscheduled. In the CSR, Subject ID should be USUBJID (not PATID) for purposes of de-identification. Sort order: Treatment Group, Subject ID, Planned Time Point.]

Treatment Group	Subject ID	Transplant Type	Duration of Symptoms	Planned Time Point	Actual Study Day	Temperature (°F)	Systolic Blood Pressure (mmHg)	Diastolic Blood Pressure (mmHg)	Heart Rate (beats/min)	Respiratory Rate (breaths/min)	Weight (kg)	Height (cm)

Listing 28: 16.2.8.3.1: Hospitalizations

Treatment Group	Subject ID	Transplant Type	Duration of Symptoms	No. of Days Post Randomization (Duration)	Diagnosis	Reason for hospitalization	Discharge Status	MedDRA System Organ Class	MedDRA Preferred Term

Listing 29: 16.8.3.2: Individual Graft Loss or Rejection Data

[Implementation Note: In the CSR, Subject ID should be USUBJID (not PATID) for purposes of de-identification.] Listing should be sorted by Treatment Group, Subject ID, Planned Time Point. If no resolution date, duration should be listing as ONGOING.]

Treatment Group	Subject ID	Transplant Type	Duration of Symptoms	Number of Days Post Randomization (Duration)	Event Type
					Graft Loss/Graft Rejection

Listing 30: 16.8.3.3: Deaths

[Implementation Note: Cause of Death will be listed as the Cause of Death on the CRF. If multiple causes listed, Cause of Death field will be populated as “Primary/Secondary/Tertiary/Quaternary/Quinary”. Listing should be sorted by Treatment Group, Subject ID, Planned Time Point.]

Treatment Group	Subject ID	Transplant Type	Duration of Symptoms	Number of Days Post Randomization	Cause of Death
					Primary/secondary/etc.

16.2.8.4 Physical Exam Findings

Listing 31: 16.2.8.4.1: Physical Exam Findings

[Implementation Note: This listing includes all physical exam findings, scheduled and unscheduled. If a subject does not have any findings upon examination, they will not be included in this listing. If reported as an AE, display “Yes” with the AE Number in parentheses, e.g., “Yes (7)”. In the CSR, Subject ID should be USUBJID (not PATID) for purposes of de-identification. Sort order: Treatment Group, Subject ID, Planned Time Point.]

Treatment Group	Subject ID	Transplant Type	Duration of Symptoms	Planned Time Point	Actual Study Day	Body System	Abnormal Finding	Reported as an AE? (AE Description; Number)

16.2.8.5 Concomitant Medications

Listing 32: 16.2.8.5.1: Concomitant Medications

[Implementation Note: “Medication Start Day” and “Medication End Day” are relative to enrollment (which is Day 1, day before enrollment is Day -1). For medication start dates that are > 30 days prior to enrollment, rather than use exact study days, categorize as follows:

- 5 years prior to enrollment
- 1-5 years prior to enrollment
- 1-12 months prior to enrollment

If ongoing, display “Ongoing” in the “Medication End Day” column. If taken for an AE or MH, display “Yes” with the AE or MH Number in parentheses, e.g., “Yes (7)”. In the CSR, Subject ID should be USUBJID (not PATID) for purposes of de-identification. Sort order: Treatment Group, Subject ID, and CM Number.]

Treatment Group	Subject ID	Transplant Type	Duration of Symptoms	CM Number	Medication	Medication Start Day	Medication End Day	Indication	Taken for an AE? (AE Description; Number)	Taken for the treatment of Norovirus?	ATC Level 1 (ATC Level 2)

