5.2 Subject Exclusion Criteria

Subjects meeting any of the exclusion criteria at baseline will be excluded from study participation

1. Other identified infectious causes of diarrhea at screening*.
2. Any condition that would, in opinion of the Site Investigator, place the subject at an unacceptable risk of injury or render the subject unable to meet the requirements of the protocol.
3. Subjects receiving oral or intravenous immunoglobulin therapy concurrently or in the 14 days prior to enrollment.
4. Nitazoxanide use for any illness in the previous 30 days prior to randomization.
5. Have received experimental products within 30 days prior to the study entry or plan to receive experimental products at any time during the study
6. Known sensitivity to nitazoxanide or any of the excipients comprising the nitazoxanide tablets.
7. Subjects unable to swallow oral medications.
8. Subjects with ostomy.
9. Women who are pregnant or lactating or have a positive urine pregnancy test at screening/enrollment/Day 1.

Co-enrollment in other studies is allowed if none of the above exclusion criteria are met.

*Alternative diagnosis requiring treatment would be considered a co-infection; if the testing is positive for a pathogen that the PI does not feel is causing the symptoms, they may be included but the PI or his/her designee must document that the positive test is not clinically significant, does not require treatment and is not causing the symptoms making the patient eligible for enrollment.

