6.6 Concomitant Medications/Treatments

Subjects may receive any therapy that is deemed appropriate to treat the signs and symptoms of Norovirus after randomization at the discretion of their treating provider except for nitazoxanide and oral immunoglobulin. This can include:

- Intravenous immunoglobulin
- Changes in immunosuppression
- Anti-motility agents

Any treatment utilized should be included on the concomitant medications at the time of enrollment. Any concomitant medication pre- or post-randomization that is being used to treat the signs or symptoms of Norovirus should be marked as such on the Case Report Form for the entire duration of the study. Likewise, any change to immunosuppressive therapy would have a

note in the Case Report Form noting if the change was made because of elevated drug levels, for treatment of Norovirus or for other purposes. Concomitant medications will be collected through visit 12 (Day 180 after initial dose of study treatment) or early termination, whichever occurs first. If the Investigator learns that the subject has taken a prohibited medication (see inclusion/exclusion criteria) prior to the last dose, the Investigator will contact the DMID Medical Officer and CPM for instructions regarding the subject's continuation in the study.

Medications that might interfere with the evaluation of the investigational product should not be used unless absolutely necessary.

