11.4.3 Efficacy Analyses

11.4.3.1 Analysis of Primary Outcome Measure

The primary efficacy outcome measure is the time from randomization to initial clinical resolution of Norovirus for at least 48 hours, assessed through 180 days, in each study arm. Clinical resolution will be assessed from the daily diary by the subject and will be defined as:

- a. Cessation of vomiting and
- b. No stools classified by the Bristol Stool Chart as diarrhea (Type 6 or 7)

The primary efficacy outcome measure will be assessed in the mITT population. Subjects who receive additional treatment with nitazoxanide other than their assigned study product will be considered censored at 180 days. To assess the effect of the choice of analysis population and additional treatment, the analysis will be repeated as a secondary analysis in the PP population. Sensitivity analyses may be performed to further assess the effect of additional treatment. The details of any sensitivity analyses will be detailed in the Statistical Analysis Plan.

The null hypothesis that the time to first clinical resolution of Norovirus is the same in both treatment arms will be tested using a stratified Log-Rank test to take into account the stratification at randomization. Estimates for median time to resolution and corresponding 95% confidence intervals will be reported for each treatment arm.

We will consider 80% compliance across the monitoring period acceptable [missing no more than 1.5/7 days per week over an 8 week period]. While we will not exclude patients, who are below this compliance for any monitoring period, we will conduct a sensitivity analysis comparing those with few missing values to those with 2 or more missing values per week.

With respect to missing data for the primary endpoint, the primary analysis will be handled as follows:

- Data that are missing after a subject has reached clinical resolution will not affect the primary time to event analysis and therefore will be ignored
- Subjects who drop out, are lost to follow-up, withdraw consent, or otherwise stop completing daily diary entries before clinical resolution will be censored on the day of their last completed diary
- Subjects with a gap in outcome data prior to clinical resolution will be handled depending on their last completed diary entry and their next completed diary entry:

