3.3. Study Definitions and Derived Variables

Diarrhea:

Diarrhea will be defined as Type 6 or 7 on the Bristol Stool chart.

Baseline Value:

The baseline value will be defined as the last value obtained prior to the first dose of study product unless otherwise noted.

Additional Nitazoxanide:

Any nitazoxanide reported as a concomitant medication will be considered additional nitazoxanide.

Initial Clinical Resolution of Norovirus Symptoms:

Clinical resolution of Norovirus symptoms will be assessed from the daily diary by the subject and will be defined as:

- Cessation of vomiting and,
- No stools classified by the Bristol Stool Chart as diarrhea (Type 6 or 7).

Subjects will need to have at least two consecutive daily diary entries where they reported no vomiting, no Bristol Stool Type 6, and no Bristol Stool Type 7 to meet the criteria for initial clinical resolution. There are several variables in the daily diary that indicate whether the subject had diarrhea or vomiting for that day.

Daily Diary Diarrhea Questions:

- Phase 1 (Treatment Phase):
 - Number of Bristol Type 6 stools? (Quantitative)
 - Were there too many Bristol Type 6 stools to count? (Qualitative)
 - Number of Bristol Type 7 stools? (Quantitative)
 - Were there too many Bristol Type 7 stools to count? (Qualitative)
- Phase 2 (Longitudinal Phase):
 - Did you have diarrhea today? (By diarrhea, we mean at least ONE bowel movement that could be described as Type 6 or 7.) (Qualitative)

Daily Diary Vomiting Questions:

- Phase 1 (Treatment Phase):
 - Did you have to take another dose because you threw up the first dose within 1 hour? (Qualitative)
 - How many times did you vomit today? (Quantitative)
- Phase 2 (Longitudinal Phase):
 - Did you vomit today? (Qualitative)

For a day to count towards clinical resolution during the treatment phase, the following responses must be recorded in the daily diary entry:

- Both quantitative diarrhea questions must be 0

- Both qualitative diarrhea questions must be missing (i.e. not “yes”)
- The quantitative vomiting questions must be 0
- The qualitative vomiting question must be “no”

For a day to count towards clinical resolution during the longitudinal phase, the following responses must be recorded in the daily diary entry:

- The qualitative diarrhea question must be “no”
- The quantitative vomiting question must be 0

If a daily diary entry is missing, refer to the imputation rules in Section [6.5](#).

Viral Load:

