6.3.2. Per Protocol (PP) Population

The PP population will include all subjects who met all inclusion/exclusion criteria, complied with the assigned study product, complied with the daily diary, and were followed up until resolution of symptoms, or completed 180 days without resolution of symptoms.

A subject is considered to be compliant with the assigned study product if he/she takes at least 75% of the scheduled doses through 28 days and does not receive additional nitazoxanide (defined as in [Section 3.3](#)) before their primary outcome is observed. A subject is compliant with the daily diary if he/she is missing no more than 1.5/7 days per week over the first 8 weeks (Day 1 through Day 60).

This analysis set will be used for all efficacy analyses and will be considered secondary to analyses conducted in the mITT population.

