16.2.5 Compliance Data

Listing 8: 16.2.5.1: Treatment Compliance Data

[Implementation Note: Each subject will have a single row in the listing. The final pill count column will contain the last pill count entered in the Treatment Dispensing Log. The Dose(s) Missed column will list all doses missed per the subject's daily diary.]

[Implementation Note: Sort order: Treatment Group, Subject ID, Dose Number.]

Treatment Group	Subject ID	Transplant Type	Duration of Symptoms	Final Pill Count ^a	Dose(s) Missed ^b
					[e.g., Day 3, Day 3 AM, etc.]

^a Final pill count will include Day 28 and Day 60 pill counts. Subjects with pill counts at both visits will use the Day 60 pill count as the final pill count.

^b Dose(s) Missed includes all missed doses per the subject's daily diary. Day X AM = Missed Day X Morning Dose; Day X PM = Missed Day X Evening Dose; Day X = Missed Both Doses on Day X.

Listing 9: 16.2.5.2: Daily Diary Compliance Data

[Implementation Note: Sort order: Treatment Group, Subject ID, Dose Number.]

Treatment Group	Subject ID	Transplant Type	Duration of Symptoms	Phase	Week Number	Number of Diaries Missed	Day(s) Missed
				Treatment/Longitudinal			[e.g., Day 3, Day 5, etc.]

Note: Weeks are only included if at least one diary was missed for that week.

Listing 10: 16.2.5.3: Daily Diary Time of Completion Compliance Data – Treatment Phase

[Implementation Note: Sort order: Treatment Group, Subject ID, Dose Number.]

Treatment Group	Subject ID	Transplant Type	Duration of Symptoms	Number Completed between 6am and 12pm	Number Completed between 12pm and 6pm	Number Completed between 6pm and 12am	Number Completed between 12am and 6am	Number Completed Less than 12 Hours after Previous Diary Completed

Listing 11: 16.2.5.4: Individual Additional Nitazoxanide Data

[Implementation Note: Additional Doses of Nitazoxanide will be based on records of Nitazoxanide on the concomitant medication form.]

[Implementation Note: In the CSR, Subject ID should be USUBJID (not PATID) for purposes of de-identification.] Listing should be sorted by Treatment Group, Subject ID, Planned Time Point.]

Treatment Group	Subject ID	Transplant Type	Duration of Symptoms	Number of Days Post Randomization (Duration)	Number of Additional Doses Taken

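### SAP 3.3 puts no date limit on additional nitazoxanide, so an eligible subject's finished pre-trial course, if recorded as a concomitant medication, would count as re-treatment.

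*SAP*

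**What the plan says.** SAP 3.3 defines the term by where the record sits, not by when the drug was taken: "Any nitazoxanide reported as a concomitant medication will be considered additional nitazoxanide". The note to Listing 11 names the same source: "Additional Doses of Nitazoxanide will be based on records of Nitazoxanide on the concomitant medication form".

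Exclusion criterion 4 (protocol 5.2, repeated in SAP 4.3) is limited in time: "Nitazoxanide use for any illness in the previous 30 days prior to randomization". Use before that window does not exclude.

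On what goes on the form, protocol 6.6 says "Any treatment utilized should be included on the concomitant medications at the time of enrollment", and asks that drugs used against norovirus be marked whether they fall before or after randomization. The note to Listing 32 (SAP Appendix 3, 16.2.8.5) covers old entries: "For medication start dates that are > 30 days prior to enrollment, rather than use exact study days, categorize as follows". Its categories reach back to 5 years.

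The flag has these uses:
- SAP 6.3.2 counts a subject as compliant with study product only if "he/she takes at least 75% of the scheduled doses through 28 days and does not receive additional nitazoxanide" before the primary outcome is seen. It points to SAP 3.3 for the meaning of the term.
- SAP 6.4, again pointing to 3.3, drops flagged subjects from a sensitivity analysis of the primary and secondary outcomes.
- SAP 9.2 and Table 6 count subjects with any additional nitazoxanide and, separately, those with additional nitazoxanide after Day 28.
- Protocol 11.4.3.1 has a rule in its own words: "Subjects who receive additional treatment with nitazoxanide other than their assigned study product will be considered censored at 180 days". SAP 5 repeats it in the power discussion.

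**The concern.** The definition is meant to pick out open-label nitazoxanide taken during the trial, which can blur the comparison of the arms. A course finished before the trial is a baseline characteristic and cannot do that. The SAP 3.3 rule does not separate the two, and eligibility does not remove the second kind. Subjects with long-standing symptoms seem the likeliest to have had an earlier course.

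At stake are membership of the per-protocol set, the content of one sensitivity analysis and a count in the disposition table. All three would depend on whether a site happened to record an old course. If the protocol's Day 180 censoring used the same flag, a subject who truly resolved would be analyzed as unresolved.

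**Working it through.** **1. Who could be affected.** Criterion 4 excludes anyone who used nitazoxanide in the 30 days before randomization. An eligible subject therefore cannot be taking it at enrollment. Any earlier exposure must be a finished course that ended before the 30-day window.

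**2. Can a finished course reach the form?** The form itself is not in the documents, and the text points both ways.

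Against:
- SAP 9.1.2 summarizes drugs started before dosing and still continuing at dosing.
- SAP 9.8 speaks of drugs taken during the study.
- Protocol 6.6 speaks of treatment in use.
- The old start dates in Listing 32 fit long-running drugs still being taken.

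Leaving it open:
- Protocol 6.6 and SAP 4.4.7 refer to norovirus drugs before as well as after randomization.
- SAP 9.8 and the title of Table 115 include prior medications.
- Listing 32 counts both start and end days from enrollment and defines Day -1.

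No passage requires or forbids the entry.

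**3. What follows if it is recorded.**
- *Per-protocol set.* A course before randomization always precedes the primary outcome, so the subject always fails SAP 6.3.2.
- *Sensitivity analyses.* The subject is left out of the additional-nitazoxanide parts of Tables 18, 23, 24, 27 and 28.
- *Table 6.* The subject is counted under any additional nitazoxanide.
- *Primary mITT analysis.* SAP 8.1 and 6.5 contain no re-treatment censoring, so the flag changes nothing there unless the protocol 11.4.3.1 rule is applied with it.

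**4. Size of one misclassification.** 1/31 = 3.2% of those enrolled (31 from SAP 6.6).

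**5. Illustration, only if Day 180 censoring is applied.** First, the plan's own figure. Exponential times with medians of 135 and 67.5 days (SAP 5) and 180 days of follow-up give resolution probabilities of 1 − 2^(−180/135) = 0.603 and 1 − 2^(−180/67.5) = 0.843, mean 0.723. With 128 subjects that is 128 × 0.723 = 92.5 events. The Schoenfeld power is Φ(ln 2 × √92.5 / 2 − 1.96) = Φ(1.37) = 91.5%. A log-rank simulation with 64 per arm also gives 91.5%, against 91.3% in SAP Table 2.

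The same model was then run with 31 subjects, assuming a 16 versus 15 split, a true hazard ratio of 2, and flagged subjects chosen regardless of outcome and set to unresolved at Day 180 (unstratified log-rank test and Cox model, at least 4,000 trials per row):

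| Flagged, nitazoxanide / placebo | Median hazard ratio | Power |
|---|---|---|
| 0 / 0 | about 2.0 | about 38% |
| 1 / 0 | about 1.7 | about 22% |
| 2 / 0 | about 1.5 | about 13% |
| 0 / 1 | about 2.2 | about 45% |
| 0 / 2 | about 2.5 | about 53% |
| 2 / 2 | about 1.9 | about 24% |

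The estimate moves down or up according to the arm in which the flagged subject falls. At the planned 64 per arm, flagging 5% or 10% of both arms lowers power from 91.5% to about 88% or 84%. That is of little use now, because the trial stopped at 31. Every number of flagged subjects here is assumed.

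**The case against.** The strongest reply is that the plan, read as a whole, already means use during the trial. Protocol 11.2 and SAP 5 describe additional nitazoxanide as given after 28 days. Protocol section 7 says that use beyond Day 28 is documented on the concomitant-medication form, which explains why SAP 3.3 points there. Listing 11 times the extra doses in days after randomization. The per-protocol rule concerns compliance during the study. On this view one sentence is loosely drafted and no analyst would flag an old course.

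Much of this stands. The intention is clear enough, and no subject with an earlier course appears in the documents. Three things keep the point alive. Table 6 has separate rows for any additional nitazoxanide and for use after Day 28, so the flag is wider than late rescue. The time column in Listing 11 is a display field, not a filter. SAP 9.1.2 limits what one summary covers, not what SAP 3.3 flags. A programmer who follows SAP 3.3 literally would include every nitazoxanide record.

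A reader might infer two stronger things. The first is that earlier users are in fact treated as re-treated. The documents do not support this, because the step from a finished course to an entry on the form is not shown; Listing 32 sets only how old start dates are displayed. The second is that the primary result is diluted and power lost. That also fails. It joins the SAP 3.3 definition to a protocol censoring rule that has its own wording and that SAP 8.1 and 6.5 do not carry. It also looks at one arm only, although prior use is a baseline trait that randomization can place in either.

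**Conclusion.** The rule in SAP 3.3 is wider than its purpose, and exclusion criterion 4 leaves room for the subjects it would misclassify. The consequence is conditional: it arises only if a finished course was recorded. It then falls on the per-protocol set, the additional-nitazoxanide sensitivity analyses and Table 6. It reaches the primary analysis only if the Day 180 censoring of protocol 11.4.3.1 is applied with this flag.

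The number of such subjects is unknown and may be zero. The hazard ratios and powers above illustrate an assumed scenario; they do not measure an effect shown to occur. With 31 subjects, and SAP 14.2 describing the analyses as primarily descriptive, this is a minor correction to a definition.

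**What to change.** In SAP 3.3, define additional nitazoxanide as nitazoxanide other than blinded study product, recorded as a concomitant medication, with a start date on or after the day of randomization, or started earlier and continuing past that day. The second clause would matter only for a subject enrolled in breach of criterion 4. Apply the same date filter in SAP 6.3.2, SAP 6.4, Table 6 and Listing 11. If the Day 180 censoring of protocol 11.4.3.1 is applied, use the same filtered flag there.

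A row for prior nitazoxanide in Table 11 would be informative but is optional.

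The cost is one sentence and a filter on start and end dates that Listing 32 already uses. Trial conduct does not change. If no earlier course was recorded, no result changes either.

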16.2.8.6 Pregnancy Reports

Listing 33: 16.2.8.6.1: Pregnancy Reports – Maternal Information

[Implementation Note: Only include the “Pregnancy Number” column if a subject has more than 1 pregnancy. Date of Conception will be calculated based on estimated delivery date. BMI will be calculated based on pre-pregnancy height and weight. Mother’s weight gain will be calculated based on pre-pregnancy weight and end of pregnancy weight. If a major congenital anomaly with previous pregnancy, display “Yes” and the text from the “specify” field, separated by a colon. If any substance use is reported, include a listing of substance use. If autopsy revealed an alternate etiology, display “Yes” and the text from the “specify” field, separated by a colon. If abnormality in product of conception, display “Yes” and the text from the “specify” field, separated by a colon. In the CSR, Subject ID should be USUBJID (not PATID) for purposes of de-identification. Sort order: Treatment Group, Subject ID, Pregnancy Number.]

	Subject ID	Pregnancy Number	Study Day Corresponding to Estimated Date of Conception	Source of Maternal Information	Pregnancy Status	Mother’s Pre-Pregnancy BMI	Mother’s Weight Gain During Pregnancy	Tobacco, Alcohol, or Drug Use During Pregnancy?	Medications During Pregnancy?	Maternal Complications During Pregnancy?	Maternal Complications During Labor, Delivery, or Post-Partum?

Note: Maternal Complications are included in the Adverse Event listing. Medications taken during pregnancy are included in the Concomitant Medications Listing.

Listing 34: 16.2.8.6.2: Pregnancy Reports – Gravida and Para

Subject ID	Pregnancy Number	Gravida	Live Births									Still Births	Spontaneous Abortion/ Miscarriage	Elective Abortions	Therapeutic Abortions	Major Congenital Anomaly with Previous Pregnancy?
			Extremely PB ^a	Very Early PB ^a	Early PB ^a	Late PB ^a	Early TB ^b	Full TB ^a	Late TB ^a	Post TB ^a						

Note: Gravida includes the current pregnancy, para events do not.

^a Preterm Birth
^b Term Birth

Listing 35: 16.2. 8.6.3: Pregnancy Reports – Live Birth Outcomes

Subject ID	Pregnancy Number	Fetus Number	Pregnancy Outcome (for this Fetus)	Fetal Distress During Labor and Delivery?	Delivery Method	Gestational Age at Live Birth	Size for Gestational Age	Apgar Score, 1 minute	Apgar Score, 5 minutes	Cord pH	Congenital Anomalies?	Illnesses/ Hospitalizations within 1 Month of Birth?

Note: Congenital Anomalies are included in the Adverse Event listing.

Listing 36: 16.2. 8.6.4: Pregnancy Reports – Still Birth Outcomes

Subject ID	Date of Initial Report	Fetus Number	Pregnancy Outcome (for this Fetus)	Fetal Distress During Labor and Delivery?	Delivery Method	Gestational Age at Still Birth	Size for Gestational Age	Cord pH	Congenital Anomalies?	Autopsy Performed?	If Autopsy, Etiology for Still Birth Identified?

Listing 37: 16.2. 8.6.5: Pregnancy Reports – Spontaneous, Elective, or Therapeutic Abortion Outcomes

Subject ID	Date of Initial Report	Fetus Number	Pregnancy Outcome (for this Fetus)	Gestational Age at Termination	Abnormality in Product of Conception?	Reason for Therapeutic Abortion
